#### 4.2.8.4 Primary Analysis of Secondary Endpoint

The analysis of OS is based on the safety population. The number and percentage of participants experiencing an OS event and Kaplan-Meier plots of OS are presented. The median OS and two-sided 90% CI are estimated using the Kaplan-Meier method if participant numbers allow. Summaries of the number and percentage of participants who have died, those still in survival follow-up, those lost to follow-up and those who have withdrawn consent are provided.

The proportion of participants alive at 3, 6, 9 and 12 months (OS-3, OS-6, OS-9, and OS-12) and associated two-sided 90% CI are estimated using the Kaplan-Meier method.

A summary of the duration of follow-up for OS is included using median (range). This is presented separately for censored and non-censored participants.

#### **4.2.8.5 Sensitivity Analyses of the secondary endpoint**

Sensitivity analysis is NA.

#### **4.2.8.6 Supplementary Analyses of the secondary endpoint**

Supplementary analysis is NA.

#### **4.2.8.7 Subgroup analyses**

Subgroup analyses is defined in section [4.2.2.6](#)

### **4.2.9 Secondary Endpoint: Changes in ctDNA from baseline**

Changes in CtDNA from baseline is a secondary endpoint.

#### **4.2.9.1 Definition and Derivations**

Change in ctDNA is defined as the percentage change in ctDNA from baseline to each timepoint for the safety population.

#### **4.2.9.2 Derivations**

Percentage change in ctDNA from baseline to each post baseline timepoint as well as the maximum change are analyzed descriptively on the Safety Population.

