7 DISCONTINUATION OF STUDY INTERVENTION AND PARTICIPANT DISCONTINUATION/WITHDRAWAL

7.1 Discontinuation of Study Intervention

It may be necessary for a participant to permanently discontinue (definitive discontinuation) study intervention. If study intervention is permanently discontinued, the participant will remain in the study to be evaluated for safety to the end of the 90-day follow-up period (Section 8.2.7), or withdrawal of consent or starting another anti-cancer therapy, whichever is earlier. Participants will be evaluated for efficacy until documented disease progression or withdrawal of consent, whichever is earlier. Participants will be followed for subsequent anti-cancer therapy until withdrawal of consent or death, whichever is earlier. See the relevant Substudy SoA for data to be collected at the time of discontinuation of study intervention and follow-up and for any further evaluations that need to be completed.

Note that discontinuation from study intervention is NOT the same as a withdrawal from the study.

The participant should continue attending subsequent study visits and data collection should continue according to the CSP. If the participant does not agree to continue in-person study visits, a modified follow-up must be arranged to ensure the collection of endpoints and safety information. This could be a telephone contact with the participant for the follow-up visit, a contact with a relative or treating physician, or information from medical records. The approach taken should be recorded in the medical records. A participant who agrees to modified follow-up is not considered to have withdrawn consent or to have withdrawn from the study.

Participants may be discontinued from study intervention in the following situations:

- Objective disease progression assessed by Investigator (a confirmatory scan for disease progression is up to the Investigator's discretion).
 - **Note:** If the participant has been discontinued from the AZD8853 intervention before disease progression, it is required for disease assessment to continue (see the relevant Substudy SoA), until documented disease progression.
- Adverse event as defined in Section 8.3.
- Participant or Investigator decision. The participant is free to discontinue treatment at any
 time, without prejudice to further treatment. When the reason does not impact safety, the
 Study Physician together with the Investigator will consider the risk/benefit to the

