Percentage change in ctDNA from baseline to each post baseline timepoint as well as the maximum change will be analysed descriptively on the Safety Population.

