Thyroid function tests (TSH, free T4, free T3) ^d	X	X			8.2.5
Urinalysis	X	X			8.2.5
Coagulation parameters (PT/aPTT/INR/d-Dimer/Fibrinogen)	X	X			8.2.5
Pregnancy test (WOCBP) °	X	X	X		8.2.5
Virology (Hepatitis B and C) ^f		X			8.2.5
Biomarker Evaluations		1		. 	
CCI	Collect on progression				10.8.6.1.3

Study Period	ЕОТ	Follow-u	p Post EOT	LTFU	Details in	
Procedure/Study Day		Day 30 (± 7 days)	Day 90 (± 7 days)	Q12W Post Day 90 Visit	Section	
		Post EOT	Post Last Dose			
Serum for GDF15 target engagement	X	X	X		10.8.5.3.1	
Whole blood for CCI (refrigerated)	X	X	X		10.8.6.4	
Whole blood for flow cytometry	X	X	X		10.8.6.5	
CCI	X	X	X		10.8.6.3	
CCI	X	X	X		10.8.6.7	
CCI	X	X	X		10.8.6.7	
Plasma for circulating tumour DNA	X	X	X		10.8.6.6	
PK and Immunogenicity	 		•			
Parts A, B and C: AZD8853 PK			X		10.8.5.1 Table 18	
AZD8853 ADA	X	X	X		10.8.5.2 Table 19	
EOT and Follow-up Assessment	'	'	•			
Subsequent anti-cancer therapy	X	X	X	X	8.2.8	
Survival status (by telephone, email, or clinic visit)	X	X	X	X	8.2.8	

To include CT or MRI slices through T12 and L3.

Abbreviations: ADA = antidrug antibody; AE = adverse event; aPTT = activated partial thromboplastin time; CT = computerized tomography; DNA = deoxyribonucleic acid; ECG = electrocardiogram; ECOG = Eastern Cooperative Oncology Group; EOT = end of treatment; GDF15 = growth differentiation factor 15; INR = international normalised ratio; LTFU = long Term Follow-up; MRI = magnetic resonance imaging; NSCLC = non-small-cell lung cancer; CC | PK = pharmacokinetics; PT = prothrombin time; Q12W = every 12 weeks; RNA = ribonucleic acid; RECIST = Response Evaluation Criteria in Solid Tumours; SAE = serious adverse event; T3 = triiodothyronine; T4 = thyroxine; TSH = thyroid-stimulating hormone; WOCBP = woman of childbearing potential.

b If CT or MRI scan for disease assessment is performed ≤ 14 days prior to the EOT visit, it will not be required at EOT visit.

^c Will not be performed if previously confirmed disease progression has been documented.

d Free T4 and T3 measured if TSH is abnormal or if clinical suspicion of an AE related to the endocrine system.

^e A urine or serum pregnancy test is acceptable; if urine test is equivocal or positive then serum β-hCG testing should be performed for confirmation.

f Required for participants with a history of hepatitis B or hepatitis C.

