### **4.2.3 Best Overall response**

#### **4.2.3.1 Definition**

BOR is calculated based on the overall visit responses from each RECIST v1.1 assessment, described in Appendix A (Section [7.1](#)). It is the best response a participant has had following start of IP, but prior to starting any subsequent cancer therapy and up to and including RECIST v1.1 progression or the last evaluable assessment in the absence of RECIST v1.1 progression. Categorization of BOR is based on RECIST v1.1 using the following response categories: CR, PR, Stable Disease (SD); progressive disease; and NE.

BOR is determined programmatically based on RECIST v1.1. using all site investigator data up until the first progression event (i.e., progression or death). For participants whose progression event is death, BOR is calculated based upon all evaluable RECIST v1.1 assessments prior to death.

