##### **4.2.7.1 Definition**

This is based on RECIST v1.1 TL measurements taken at baseline and each post-baseline assessment. Tumour size is the sum of the longest diameters (or short axis measurements for

lymph nodes) of the TLs. Baseline for RECIST v1.1 is defined to be the last evaluable assessment prior to first IP dose.

An outcome endpoint for this study is percentage change from baseline in TL tumour size at each post-baseline assessment e.g., at Study week 15.

The tumour size and percentage change from baseline in the sum of tumour size at each assessment are calculated. The best change in tumour size from baseline (i.e., depth of response) is the largest decrease from baseline or the smallest increase from baseline in the absence of a reduction and includes all assessments:

- up to and including the first visit at which the overall visit response is progressive disease,
- prior to death in the absence of progression,
- prior to the start of subsequent anti-cancer therapy (including radiotherapy)
- or up to and including the last evaluable RECIST v1.1 assessment if the participant has not died, progressed, or started subsequent anti-cancer therapy.

Each post-baseline disease assessment for a participant that meets the following conditions are included: all TLs identified at baseline have measurements recorded at the current visit (i.e., they cannot be not done or not evaluable). If a lesion is recorded as  $\leq 5$ mm then this is used in the calculations.

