#### **4.2.9.3 Primary Analysis of Secondary Endpoint**

Percentage change from ctDNA from baseline to each timepoint is summarised by mean percentage change and St.Dev. Maximum change is also summaries by mean and St.Dev.

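### The ctDNA endpoint has no cut-off at subsequent anti-cancer therapy, so samples taken after a switch may enter the end-of-treatment, follow-up and maximum-change summaries

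*SAP*

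**What the plan says.** Change in ctDNA is a secondary efficacy endpoint, under an objective of assessing the efficacy of AZD8853 from longitudinal blood samples (protocol Tables 1 and 4; SAP Table 3, Objective 3).

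- **Definition, SAP 4.2.9.1:** "Change in ctDNA is defined as the percentage change in ctDNA from baseline to each timepoint for the safety population".
- **Derivation, SAP 4.2.9.2:** "Percentage change in ctDNA from baseline to each post baseline timepoint as well as the maximum change are analyzed descriptively on the Safety Population". Protocol Section 9.4.3 has the same rule in almost the same words.
- **Summary, SAP 4.2.9.3:** means and standard deviations by timepoint, and "Maximum change is also summaries by mean and St.Dev".
- **Sampling after treatment, protocol Table 14:** the row "Plasma for circulating tumour DNA" is marked at EOT, Day 30 post EOT and Day 90 post last dose. It has no footnote. The scan rows do have one, which drops the Day 90 and later scans once confirmed progression has been documented.
- **Attendance after stopping AZD8853, protocol 7.1:** "The participant should continue attending subsequent study visits and data collection should continue according to the CSP".

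None of the ctDNA text says what to do with a sample taken after another anti-cancer therapy has begun.

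**The concern.** The endpoint is meant to describe what AZD8853 does to ctDNA. A sample drawn after a participant has moved to another drug no longer measures that. The plan foresees such switches: Table 14 records subsequent anti-cancer therapy at EOT, Day 30 and Day 90, the same visits at which ctDNA is drawn.

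The maximum change is the more exposed result. It takes one extreme value per participant across all timepoints, so a single sample after a switch can replace everything observed on AZD8853. The EOT and follow-up rows are exposed more simply, because they would average AZD8853 washout with the effect of whatever came next. The cohorts are uncontrolled and summarised descriptively, so no comparator would reveal the mixture.

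**Working it through.** The plan gives no figure to reproduce, so the check is mainly a comparison of texts.

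**Step 1. Does a general rule supply the missing cut-off?** SAP 3.3.1 limits summary tables to data up to 97 days after last dose and before subsequent cancer therapy, but only for safety data assessed at visits. SAP 4.2 names ctDNA among the efficacy analyses, so that rule does not reach it.

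**Step 2. How do the other efficacy endpoints treat subsequent therapy?**

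| Endpoint | SAP section | Rule |
|---|---|---|
| ORR | 4.2.2.1 | Cut at subsequent anticancer treatment, radiotherapy not counted |
| BOR | 4.2.3.1 | "but prior to starting any subsequent cancer therapy" |
| Stable-disease duration in DCR | 4.2.4.2 | Time after subsequent therapy excluded |
| Best tumour-size change | 4.2.7.1 | Cut at subsequent therapy, radiotherapy counted |
| Tumour size by visit | 4.2.7.2 | No exclusion stated |
| PFS, OS | 4.2.6.1, 4.2.8.1 | Counted despite another therapy, by design |
| ctDNA by timepoint and maximum | 4.2.9 | Nothing stated |

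The closest analogue of the ctDNA maximum change is the best tumour-size change, which is cut. A programmer following 4.2.9.2 literally would include every post-baseline ctDNA value.

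**Step 3. Which results are exposed?** Protocol Table 8 bars other systemic anti-cancer therapy while participants are on study intervention, so scheduled on-treatment timepoints are largely unaffected. That leaves the EOT, Day 30 and Day 90 rows and the maximum change.

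**Step 4. Scale, by assumption only.** Let f be the share of a group whose extreme value comes from a sample after a switch, and d the extra fall in percentage points on the new therapy. If maximum change means the largest decrease:

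shift in mean maximum change = -f x d

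| f | d | Shift (points) |
|---|---|---|
| 0.10 | 30 | -3 |
| 0.20 | 50 | -10 |
| 0.25 | 80 | -20 |
| 0.30 | 80 | -24 |
| 0.50 | 80 | -40 |

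The third line corresponds to 5 switchers in a group of 20: 5 x 80 / 20 = 20. The documents give neither f nor d. With a cut-off at subsequent therapy the shift is zero by construction.

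**The case against.** The strongest reply is protocol 7.1 read in full. After permanent discontinuation, safety evaluation runs through the 90-day follow-up but ends sooner if another anti-cancer therapy starts. Efficacy evaluation ends at progression or withdrawal of consent. A participant who progresses and then switches might therefore have no further ctDNA drawn. This stands as mitigation. It does not close the gap: 7.1 does not mention ctDNA or biomarker samples, the same section asks for continued visits, and someone who switches before progression remains under efficacy evaluation. It also governs conduct, not analysis, so any sample that reaches the database still falls under 4.2.9.2.

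Second, the plan has no uniform truncation rule for ctDNA to break. PFS and OS deliberately ignore subsequent therapy, and the tumour-size cut-off is attached to the best change, not to the by-visit values. This is correct. The case for cutting the ctDNA follow-up rows therefore rests on the endpoint's stated purpose, and the existing precedent covers only best-response-type measures. For PFS and OS the choice is written down; for ctDNA nothing is.

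Third, the analysis is descriptive, no hypothesis is tested, and SAP Table 1 does not list ctDNA among the interim efficacy data. That limits the consequence but does not make the rule right.

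**Conclusion.** The concern holds as a gap in the stated rule. Applied as written, SAP 4.2.9 and protocol 9.4.3 admit samples taken after a switch into the EOT and follow-up rows and into the maximum change. It should be fixed, but it does not touch the primary safety endpoints or, to any important extent, the on-treatment ctDNA rows.

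The size is unknown. Harm requires a switch before a scheduled sample, the sample being drawn, and a ctDNA change on the new therapy. For the maximum change, crediting a fall to AZD8853 also requires reading the term as the largest decrease, and the SAP gives it no direction. The 20-point example illustrates these assumptions and is not an estimate.

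Two stronger readings are not supported:

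- A reader might infer that falls caused by later drugs will be credited to AZD8853. The documents show only that they can be, because 7.1 may reduce such sampling and no switching rate is given.
- A reader might extend the point to circulating GDF15, which is sampled at the same follow-up visits. SAP 4.2.10 does not mention maximum change, although SAP Table 4 and protocol 10.9.4.4.1 do. Free GDF15 is measured for target engagement, late samples may properly describe recovery after dosing, and the documents give no reason why a later therapy would produce the largest reduction.

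**What to change.** In SAP 4.2.9:

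1. Restrict the maximum change and the EOT, Day 30 and Day 90 summaries to samples taken before the start of subsequent anti-cancer therapy. State whether radiotherapy counts, since ORR and best tumour-size change differ on this.
2. List later samples, flagged, without summarising them.
3. Define maximum change as the largest decrease from baseline, or the smallest increase if there is none, matching the definition of best tumour-size change.

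Align protocol 9.4.3 at its next amendment. No new data are needed: Table 14 already records subsequent therapy, and SAP 3.3.6 has imputation rules for incomplete start dates. Those rules generally impute late within the month or year, so samples near an imputed date should be flagged.

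The cost is a few sentences and a programming filter. There will be fewer values at the follow-up timepoints, and those rows will describe only participants who had not yet switched, which a table footnote should say.

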#### **4.2.9.3 Primary Analysis of Secondary Endpoint**

Percentage change from ctDNA from baseline to each timepoint is summarised by mean percentage change and St.Dev. Maximum change is also summaries by mean and St.Dev.

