#### 3.3.1 General Study Level Definitions

The general principles described below are followed throughout the study:

- Continuous endpoints are summarised by the number of observations, mean, standard deviation (Std Dev), median, upper, and lower quartiles (as applicable), minimum, and maximum. For data that requires log-transformation, it is more appropriate to present geometric mean, Coefficient of Variation (CV), median, minimum, and maximum. Categorical endpoints are summarised by frequency counts and percentages for each category.
- If data are available for less than three participants, no summary statistics other than minimum, maximum, and number of observations are presented.
- Unless otherwise stated, percentages are calculated out of the analysis set total (excluding efficacy and exposure) and for dose cohort by time point and tumour type as appropriate.
- For continuous data, descriptive summary statistics (mean, median, Std Dev, standard error, Confidence Intervals [CIs]) are rounded to one additional decimal place compared to the original data. Minimum and maximum are displayed with the same accuracy as the original data.
- For categorical data, percentages are rounded to 1 decimal place.
- SAS® version 9.4 (as a minimum) is used for all analyses.

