- Baseline is the last non-missing value obtained prior to the first dose/administration of any IP and any information taken after first dose/administration of IP is regarded as post-baseline information. If two visits are equally eligible to assess participant status at baseline (e.g., screening and baseline assessments both on the same date prior to first dose/administration with no washout or other intervention in the screening period), the average is taken as the baseline value. For non-numeric laboratory tests (i.e., some of the urinalysis parameters) where taking an average is not possible then the best value is taken as baseline as this is the most conservative. In the scenario where there are two assessments on Day 1 prior to first dose, one with time recorded and the other without time recorded, the one with time recorded is selected as baseline. Where safety data are summarised over time, study day is calculated in relation to date of first treatment. For assessments on the day of first dose where time is not captured, a nominal pre-dose indicator, if available, serves as sufficient evidence that the assessment occurred prior to first dose. Assessments on the day of the first dose where neither time nor a nominal pre-dose indicator are captured is considered prior to the first dose if such procedures are required by the protocol to be conducted before the first dose. If no value exists before the first dose/administration, then the baseline value is treated as missing.
- In all summaries, change from baseline endpoints are calculated as the post treatment value minus the value at baseline. The percentage change from baseline is calculated as  $(\text{post-baseline value} - \text{baseline value}) / \text{baseline value} \times 100$ . For any endpoint subjected to log transformation, the change from baseline calculated and summarised on the log scale are back-transformed and presented as a ‘baseline scaled ratio’ (BSR). Percentage change is then calculated as  $(\text{BSR} - 1) \times 100$ .
- Unless stated otherwise, two-sided CIs are produced at 90%.

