Secondary	Change in ctDNA from baseline	Safety analysis set	Percentage change in ctDNA from baseline to each post baseline timepoint is summarized by mean change and St Dev. Maximum change is	4.2.9

Statistical category	Endpoint	Population	Population level summary (analysis)	Details in section
			also summarised by mean and St. Dev.	
Objective 4: To determine the PK of AZD8853 in serum when administered in participants with selected advanced/metastatic solid tumours				
Secondary	PK parameters (include but not limited to Cmax and AUC)	PK analysis set	Summary of PK profile of AZD8853	4.2.12
Objective 5: To assess the immunogenicity of AZD8853 in participants with selected advanced/metastatic solid tumours				
Secondary	ADAs against AZD8853 in Serum	Immunogenicity analysis set	Incidence of detectable ADAs against AZD8853 in serum	4.2.13

ADA = antidrug antibodies; AUC = Area Under the Curve; AEs = Adverse Events; CI= Confidence Interval; ctDNA = circulating tumour deoxyribonucleic acid; DCR= disease control rate; DLT= dose limiting toxicity; DoR=duration of response; ECG= Electrocardiogram; MTD = Maximum Tolerated Dose; OS= overall survival; ORR=objective response rate; PFS=Progression Free Survival; PK =pharmacokinetics; RECIST = Response Evaluation Criteria in Solid Tumours v1.1; RP2D = Recommended Phase 2 Dose; SAEs = Serious Adverse Events; St. Dev = Standard Deviation.

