##### **4.2.11.2 Primary Analysis of Secondary Endpoint**

The change in CD8 tumour infiltration measured by IHC will be summarised using descriptive statistics, standard summary statistics n, mean, St. Dev, median, minimum, and maximum will be presented.

Summary of absolute values and percent change from baseline will be produced.

Listing of individual values is provided.

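### The ctDNA section names only the mean and SD of percentage change, a scale on which one large rise can outweigh several falls, and gives no rule for undetectable values

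*SAP*

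**What the plan says.** SAP 4.2.9.3, the analysis section for this endpoint, reads: "Percentage change from ctDNA from baseline to each timepoint is summarised by mean percentage change and St.Dev". It adds: "Maximum change is also summaries by mean and St.Dev". Table 3 repeats the rule: "Percentage change in ctDNA from baseline to each post baseline timepoint is summarized by mean change and St Dev". Neither place names a median, a geometric mean or a log scale, and neither says whether the maximum change means the largest fall, the largest rise or the largest absolute change.

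SAP 3.3.1 gives the formula: "The percentage change from baseline is calculated as" (post-baseline - baseline) / baseline x 100. The same section sets general rules. One reads: "Continuous endpoints are summarised by the number of observations, mean, standard deviation (Std Dev), median, upper, and lower quartiles (as applicable), minimum, and maximum". Another reads: "For data that requires log-transformation, it is more appropriate to present geometric mean, Coefficient of Variation (CV), median, minimum, and maximum". For change from baseline it adds: "For any endpoint subjected to log transformation, the change from baseline calculated and summarised on the log scale are back-transformed" and reported as a baseline scaled ratio (BSR), with percentage change then equal to (BSR - 1) x 100. No section says whether ctDNA is such an endpoint.

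Protocol 9.4.3 asks only for a descriptive analysis of percentage change and maximum change in ctDNA on the Safety Population. The protocol's general default in 9.4.1 includes the median, minimum and maximum. Rules for non-quantifiable values appear in the SAP only for PK concentrations (4.2.12).

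**The concern.** Percentage change treats falls and rises unequally. A halving is -50% and a doubling is +100%, so the two average +25% instead of cancelling. A complete clearance counts as -100%, while a rise can count for any amount. The groups are small: 3 to 9 per dose cohort in Part A and about 10 per dose level and indication in Part B. In groups of that size one participant with rapid progression can set the sign of the mean and inflate the SD.

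The second gap is at the detection limit. ctDNA sampling is mandatory for all participants (protocol 10.8.6.6), and the visible inclusion criteria do not require detectable ctDNA. If an undetectable baseline is recorded as zero, the formula divides by zero, so a participant who goes from undetectable to detectable has no defined value. One who goes the other way counts as -100%. If undefined values are simply left out, only rises are lost. The choice would fall to programming, possibly after the data are seen.

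With no hypothesis test, the descriptive summary is the whole result for this endpoint. A misleading headline figure would not be corrected by a later analysis.

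**Working it through.** The documents give no expected value, SD or sample-size argument for ctDNA, so there is no planned figure to reproduce. The check applies the SAP 3.3.1 formula.

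**Example without a distributional assumption.** Take four participants with changes -90%, -75%, -50% and +500%, that is, ratios 0.1, 0.25, 0.5 and 6.
- Mean: (-90 - 75 - 50 + 500) / 4 = +71%.
- Median: (-75 - 50) / 2 = -62.5%.
- Geometric mean ratio: (0.1 x 0.25 x 0.5 x 6)^(1/4) = 0.075^(1/4) = 0.523, a change of -48%.

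**Ten participants, nine of whom halve.** If the tenth rises k-fold, the mean is [9 x (-50) + 100 x (k - 1)] / 10. It is 0% at k = 5.5 and +45% at k = 10 (SD 300). The median is -50% in both cases. At k = 10 the geometric mean change is -32.5%.

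**How often this could happen (illustrative).** Assume that the ratio post/baseline is log-normal with median 0.5 (a true median change of -50%) and log-SD s. The expected mean percentage change is 100 x (0.5 x exp(s²/2) - 1), which is above zero when s > sqrt(2 ln 2) = 1.18. The last three columns come from 100,000 simulated groups for each row.

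| s | Expected mean | n = 10: mean above 0 with the group's own median below 0 | n = 40: same | n = 10: geometric mean change above 0 |
|---|---|---|---|---|
| 0.5 | -43.3% | 0.0% | 0.0% | 0.0% |
| 0.8 | -31.1% | 6.7% | 0.6% | 0.3% |
| 1.0 | -17.6% | 19.7% | 14.2% | 1.4% |
| 1.18 | 0% | 32.8% | 42.9% | 3.2% |
| 1.5 | +54.0% | 49.4% | 82.5% | 7.2% |
| 2.0 | +269.5% | 60.3% | 94.4% | 13.7% |

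Above s of about 1.18 a larger group does not help, because the mean then settles on a positive value.

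**Sensitivity of the alternative.** If nine of ten participants are unchanged and one falls 1000-fold to a substituted limit, the geometric mean ratio is 0.001^(1/10) = 0.50, a change of about -50%, while the median is 0%. With a limit that allows only a 100-fold fall it is 0.01^(1/10) = 0.63, or -37%. The geometric mean therefore depends on the substituted value.

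**The case against.** The strongest reply is that the median is already planned. SAP 3.3.1 applies throughout the study and gives continuous endpoints the median, minimum and maximum, with quartiles as applicable; protocol 9.4.1 agrees. In the four-person example the table would then show -62.5% beside +71%, with the +500% visible. Table 3 also looks like shorthand: it names only the mean and SD for tumour size, yet SAP 4.2.7.3 reports the median. A reader might infer that the trial will publish nothing but a mean and SD for ctDNA. The documents do not support that. What remains is that 4.2.9.3 itself names only the mean and SD, whereas the GDF15 section (4.2.10.2) lists the median and range. A median also leaves the zero baseline unresolved.

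The geometric route is open too: SAP 3.3.1 provides it, and protocol 10.9.4.4.1 allows geometric means for biomarker analyses. But that is permission in a pharmacodynamics section, and nothing assigns ctDNA to it.

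A reader might also infer that the mean will have the wrong sign. The documents give no ctDNA variability, and at a log-SD of 0.5 a reversal almost never occurs. Even where it occurs under the log-normal model, the arithmetic mean really is positive. The issue is which summary describes the typical participant, and the calculation itself is not in error.

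A further temptation is to extend the point to CD8 infiltration, where SAP 4.2.11.2 says: "Summary of absolute values and percent change from baseline will be produced". That does not hold, because the same section already lists the median, minimum and maximum.

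Finally, the stakes are modest. There is no hypothesis and no comparison between cohorts. The Part C interim efficacy list in SAP Table 1 omits ctDNA, and no decision rule in the visible text uses it.

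**Conclusion.** The point holds as a gap in how the endpoint is specified. The ctDNA section and Table 3 name a summary that one large rise can dominate, nothing assigns ctDNA to the log-scale method already in the SAP, and no rule covers undetectable samples. These three statements rest on the text and on arithmetic.

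The size is uncertain. The simulated frequencies rest on an assumed log-normal ratio and an assumed true median of -50%, and they run from almost never to more than half of ten-participant groups as log-SD goes from 0.5 to 2.0. The share of participants with undetectable baseline ctDNA is unknown, and so is the way the assay reports such samples. The general rule that adds the median lessens the problem. Error rates, sample size and visible decision rules are unaffected. The change is worth considering because it is cheap.

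**What to change.** In SAP 4.2.9 and Table 3:
- Name two summaries for ctDNA at each timepoint and for the maximum change: the median with quartiles and range, and the geometric mean BSR of SAP 3.3.1 shown as (BSR - 1) x 100 with a two-sided 90% CI.
- Enter undetectable samples, at and after baseline, at an assay-limit value fixed before the data are reviewed, so that participants with an undetectable baseline stay in.
- Report the number who go from detectable to undetectable and the number who go from undetectable to detectable.
- Define the direction of the maximum change.

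The cost is SAP wording and a little programming, with no new data. The downside is that the geometric mean depends on the substituted value, which is why the median should stand beside it.
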